The device employs a soft neoprene/nylon headband to fix the ear covers in place, with multiple sizes of both the ear covers and headbands to accommodate multiple sizes of infants.^{FIG 3} A patent for the device is pending. Recent Food and Drug Administration rulings have waived a requirement for an Investigational Device Exemption (“IDE”) for this type of device (see attached letter).

FIG 3. NEATCAP prototype noise protection device on premature infant model. illustrating circumaural ear covers. fabric band and

Phase 1 of the study will entail a 60-minute initial size and fit evaluation of the device on a

convenience sample of 25 infants admitted to the NICU. The inclusion criteria for the study include study initiation during the first two (2) weeks of NICU hospitalization and written signed informed consent from the parents of the study subjects. Exclusion criteria will include: age less than 12 hours, significant cranial trauma noted on admission, congenital anomalies of the head and/or neck, hemodynamic instability requiring pharmacologic intervention and a recommendation by the attending neonatologist not to enroll the patient for any reason.

In Phase 1, the device will be applied by a single trained senior neonatal intensive care nurse with experience in recognizing distress in NICU patients. Once proper fit of the device has been assured, it will be removed and a 30 minute “time out” interval will be employed. Baseline vital signs will then be obtained (see attached data collection sheet), the device will be re-applied and repeat vital signs will be obtained at 30- and 60-minute time periods. The device will be removed after 60 minutes and a fourth set of vital signs will be obtained 30 minutes after device removal. The primary endpoint of the study will be the absence of any device-related adverse events, including evidence of skin discomfort or irritation at the site of device application, or significant sustained changes in vital signs consistent with a stress response, as outlined in Table #1.

Table #1.

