
Significant elevated stress is defined as persistence of any of the following in the absence of intrusive manipulations of the patient (e.g.: IV insertions, nursing care procedures, etc.) based on the Cries Score for Pain Assessment:¹²
 
• Temperature: >0.6°F increase in temperature above baseline.• Respiration: > 20% increase in respirations per minute above baseline• Pulse: >20% increase in beats per minute above baseline• Blood pressure: >20 mm Hg increase in systolic blood pressure above baseline• Oximetry level: >5% pulse oximeter decrease below baseline	
Secondary endpoints will include NEATCAP sizing options able to fit >90% of the target population and a >80% positive response to a multi-question ease-of-use questionnaire completed by the participating NICU staff (see the attached questionnaire). The data will be stored by the Study Coordinator

--	--

and will undergo statistical analysis for repeated measures by [name], MS, with subsequent review by the primary investigator and the device consultants. If no specific negative findings are identified, Phase 2 will begin.

Phase 2 will entail a 3-day evaluation of tolerance of the device, entailing a total of three (3) eight-hour-long sessions of device use on three (3) consecutive days. The study population will consist of a convenience sample of 25 neonates with identical inclusion and exclusion criteria as outlined for Phase 1. After obtaining baseline vital signs prior to each session, the bedside NICU nurse assigned to the patient will apply the device under the supervision of the data collection RN. Temperature and blood pressure data will be obtained at 3 and 6 hours of device use and heart rate, respiratory rate and oxygen saturation levels will be recorded every hour. The device will be removed after eight hours, with continued monitoring of vital signs for another eight hours after device removal. The primary endpoint of the study will be the absence of device-related adverse events, including evidence of skin discomfort or irritation at the site of device application, or sustained changes in vital signs consistent with a stress response, as outlined in Table #1. Secondary endpoints will include a >80% positive

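### In both phases the only named analysis, an unspecified repeated-measures analysis, is not tied to the event-based primary endpoint, and no proportion of infants with an event or confidence interval is planned

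*Combined protocol and SAP*

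**What the plan says.** The combined protocol and SAP sets out both phases in its Methods section.

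- **Primary endpoint.** For Phase 1: "The primary endpoint of the study will be the absence of any device-related adverse events". Two kinds of event are then named. One is local to the skin ("including evidence of skin discomfort or irritation at the site of device application"). The other is a lasting vital-sign change that points to stress, as listed in Table #1. Phase 2 has nearly the same endpoint, without the word *any*.
- **Table #1.** "Significant elevated stress is defined as persistence of any of the following", followed by five thresholds, each relative to the infant's baseline (temperature, respiration, pulse, systolic pressure, oximetry).
- **Sample.** Phase 1 takes a "convenience sample of 25 infants admitted to the NICU"; Phase 2 takes a convenience sample of 25 neonates.
- **Analysis.** Phase 1 data are stored "and will undergo statistical analysis for repeated measures by" a named analyst, then reviewed by the primary investigator and device consultants. Phase 2 also names only repeated measures. Neither statement gives an outcome, model or contrast.
- **Progression.** "If no specific negative findings are identified, Phase 2 will begin".
- **Phase 1 sequence.** The device is first applied to check fit. "Once proper fit of the device has been assured, it will be removed", and a 30-minute pause follows. "Baseline vital signs will then be obtained", and the device is then re-applied for 60 minutes.

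The only percentage targets are for secondary endpoints: more than 90% of the target population fitted (Phase 1) and more than 80% positive questionnaire response (both phases).

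**The concern.** The endpoint asks whether device-related events occurred. The named method, in its usual use on serial vital signs, asks whether average values changed over time. These are different questions, and a few infants who cross a Table #1 threshold can be lost in an average.

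No event count, proportion or interval is planned for either phase, so the primary safety result has less numerical definition than the ease-of-use result. If no events are seen, the report could state absence without saying what event rate remains compatible with 25 infants. Two decisions rest on this result. Phase 1 opens Phase 2, which moves from 60 minutes of use to three eight-hour sessions, and Risks/Benefits says the pilot may lead to a trial of sustained use.

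**Working it through.** **Inputs.** n = 25 per phase (Methods). The documents give no significance level, expected or acceptable event rate, or precision target, so there is no planned figure to reproduce. The 95% level and the event rates below are assumptions for illustration.

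**Step 1: does an analysis of means answer the endpoint?** Assume 2 of 25 infants have a sustained 25% rise in pulse and the other 23 do not change. Both exceed the 20% threshold in Table #1, so the endpoint is not met. The mean rise is (2 × 25% + 23 × 0%) / 25 = 2%. A comparison of means could look reassuring although 2/25 = 8% of infants had an event.

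**Step 2: what does a zero-event result leave open?** For 0 of n, the exact (Clopper-Pearson) upper limits are:

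- two-sided 95%: 1 − 0.025^(1/25) = 0.137, or 13.7%
- one-sided 95%: 1 − 0.05^(1/25) = 0.113, or 11.3%

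**Step 3: how often would no events be seen if the true rate were not zero?** With independent infants, P(0 of 25) = (1 − p)^25.

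| Assumed true rate | P(no events in 25) |
|---|---|
| 2% | 0.98^25 = 60.3% |
| 5% | 0.95^25 = 27.7% |
| 10% | 0.90^25 = 7.2% |

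**Step 4: what would the proposed analysis report?**

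| Infants with an event | Proportion | Exact two-sided 95% CI |
|---|---|---|
| 0/25 | 0% | 0 to 13.7% |
| 1/25 | 4% | 0.1 to 20.4% |
| 2/25 | 8% | 1.0 to 26.0% |
| 3/25 | 12% | 2.5 to 31.2% |

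**Step 5: unit of counting.** In Phase 2, heart rate, respiratory rate and oxygen saturation are read hourly, and temperature and blood pressure at 3 and 6 hours, in each of three sessions. Readings and sessions within an infant are correlated. The binomial interval is valid for infants, each counted once, and not for readings or sessions.

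**The case against.** **It is a pilot.** It states no hypothesis and claims no safety rate. Absence of events can be read as a pass/fail criterion for the phase, which a simple count settles, and if the count and the number treated are reported a reader can derive the interval. Much of this stands: no formal test is needed, the per-infant proportion is an interpretation of the endpoint, and omitting an interval does not bias the result. But even the pass/fail reading needs an infant-level count, and no analysis statement provides for one.

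**A reader might infer that the named method cannot cover skin events.** The documents do not support that. They apply the analysis to the data in general, and repeated-measures methods exist for yes/no outcomes. What can be said is that the method is unspecified and that no serial numeric skin measure is described.

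**A reader might also infer that events at the Phase 1 fitting step would be left out, making the result look better.** The documents do not support that either. The Phase 1 endpoint covers *any* device-related event and is stated after both applications are described. No passage says that an infant irritated at fitting would stop or leave the denominator.

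**Unseen material.** The opening pages, the data collection sheet and the questionnaire are not available, so how skin findings are recorded cannot be judged. The analysis statements for both phases are available.

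**Conclusion.** The concern holds in this form: both phases have an event-based primary endpoint, the one named analysis is unspecified and not linked to it, and no infant-level proportion or interval is planned. It should be fixed, but it does not invalidate the pilot.

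The size is best seen in the most favourable result. No events in 25 infants does not exclude a true rate of up to 13.7% (upper end of a two-sided 95% interval) or 11.3% (one-sided 95% limit). This assumes independent infants, one yes/no result per infant and a 95% level chosen for illustration. In a convenience sample the interval describes sampling uncertainty only, not how well the infants represent others in the NICU. The finding does not extend to a claim of bias from the fitting step or of a method unable to handle skin events.

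**What to change.** For each phase, state as the primary analysis:

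- **Numerator:** infants with at least one device-related adverse event, given overall and separately for skin and vital-sign events, each infant counted once across readings and sessions.
- **Denominator:** all infants on whom the device was applied.
- **Precision:** an exact (Clopper-Pearson) two-sided 95% confidence interval. Any statement that no events occurred carries its upper limit, labelled as two-sided (13.7% for 0/25).
- **Phase 1 fitting step:** say expressly that events there are included, consistent with the endpoint's wording. Table #1 changes can be judged only once a baseline exists, so report how many infants had one.
- **Phase 2 baseline:** confirm that each session is compared with its own baseline, as the pre-session readings already imply.

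Keep the repeated-measures analysis of vital signs as supportive, and name its outcomes and model.

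The cost is analysis wording and one more table per phase, with no more infants. Counting vital-sign events needs a written rule for when a change is sustained, which the existing endpoint already requires. The timing of skin checks may also need stating. The drawback for the sponsor is a less favourable statement of a zero-event result.

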response to a multi-question ease-of-use questionnaire by the bedside nurse assigned to the patient and acceptance of the device by the patient's parents, by direct questioning by the principal investigator. Data for Phase 2 will be stored by the Study Coordinator with statistical analysis for repeated measures by [name], MS. All data will be de-identified by the Study Coordinator prior to analysis.

Risks/Benefits

The potential study risks to subjects include skin discomfort, irritation or pain at the site of device application and/or adverse changes in vital signs associated with device usage. The potential study benefits are to provide critical data for the product development of an optimally-designed circumaural hearing protection device for patients receiving neonatal intensive care. This pilot study will potentially lead to a trial of sustained use of this device in the NICU.

References

3. NICHD Neonatal Research Network (NRN): Extremely Preterm Birth Outcome Data. http://www.nichd.nih.gov/about/org/der/banches/ppd/programs/epbo/pages/epbo_case.aspx?start=17;31;31.

8. Liu, W. (2012). The impact of a noise reduction quality improvement project upon sound levels in the open-unit-design neonatal intensive care unit. *Journal of Perinatology*, 30, 489-496.

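### Phase 2 parent acceptance comes from the principal investigator's own direct questioning, which is open to social-desirability bias; a short written form handled by the Study Coordinator would be a cheap improvement

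*Combined protocol and SAP*

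**What the plan says.** The Phase 2 text in the Methods section of the combined protocol and SAP names two secondary endpoints. The first is a more than 80% positive "response to a multi-question ease-of-use questionnaire by the bedside nurse assigned to the patient". The second is the parents' acceptance of the device, obtained "by direct questioning by the principal investigator".

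For parents, the text mentions no form, response scale, timing, threshold or neutral interviewer. The parents concerned are those who gave written consent, which is an inclusion criterion in Phase 1 and applies identically in Phase 2.

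On numbers: "The study population will consist of a convenience sample of 25 neonates".

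On data handling: "Data for Phase 2 will be stored by the Study Coordinator with statistical analysis for repeated measures", and "All data will be de-identified by the Study Coordinator prior to analysis".

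**The concern.** The method of collection is itself stated, so this is a design choice and not a gap in the text. A parent who has agreed to the study, whose infant is or recently was in intensive care, is asked by the study's leader for a view of the study device. Some parents will be reluctant to say no, and an interviewer with an interest in the device may ask or record in a favourable way. Both effects would be expected to push the result upwards.

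The Risks/Benefits section says that the data are meant to guide product development and may lead to a trial of sustained use. An acceptance figure inflated by who asks could mislead that work. Recruiting more families would not cure it, and an answer already given to the investigator cannot be collected again neutrally.

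**Working it through.** The plan gives no figure for parent acceptance, so there is nothing to reproduce. The check has two parts.

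**1. Does anything in the plan offset the bias?**

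- De-identification takes place before analysis, and so after the parent has answered the investigator. It protects confidentiality in the dataset but cannot change the answer.
- The repeated-measures analysis concerns how recorded data are modelled. It cannot correct a shift in the answers themselves.
- The ease-of-use questionnaire is described as an attachment where Phase 1 introduces it. The sentence on parents refers to no attachment; it gives direct questioning as the whole method.

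No safeguard is found.

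**2. How much could it matter? (illustration)**

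Input from the protocol: 25 neonates, hence at most 25 families.

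Assumptions, not in the documents: all 25 families answer; true acceptance is 70%; the interviewer effect adds 0, 5, 10 or 15 percentage points; the result is summarised with an exact (Clopper-Pearson) 95% interval, which the plan does not currently call for.

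Step (a): find the smallest count whose interval excludes 70% from below.

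- 22/25 (88%): lower limit 68.8%, so 70% is still inside.
- 23/25 (92%): interval 74.0% to 99.0%, so 70% is excluded.

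Step (b): compute P(X ≥ 23) for X ~ Binomial(25, 0.70 + shift).

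| Shift (points) | Expected result | P(interval wholly above 70%) |
|---|---|---|
| 0 | 70% | 0.009 |
| 5 | 75% | 0.032 |
| 10 | 80% | 0.098 |
| 15 | 85% | 0.254 |

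With about 25 families, sampling error is also large: 20/25 accepting (80%) has an exact 95% interval of 59.3% to 93.2%. Sampling error is visible once an interval is reported. The interviewer shift is not visible in any interval, which is why it has to be dealt with at collection.

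**The case against.** **On the parents.** Direct questioning is an openly stated choice in a small pilot, and conversation can bring out comments that a short form would miss. The size of any shift is assumed, no parental threshold exists and no decision rule uses the answer. The Study Coordinator is study staff too. All of this stands, and it keeps the point minor. It does not rescue the method: the open comments can be gathered separately, and a written answer given without the investigator present is less exposed than a spoken one to the investigator.

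**A stronger reading that the documents do not support.** A reader might infer that the nurse result is also flawed. The device is used in "three (3) eight-hour-long sessions of device use on three (3) consecutive days", and "the bedside NICU nurse assigned to the patient will apply the device under the supervision of the data collection RN". With 25 × 3 = 75 sessions, one nurse could answer several times, and treating 75 forms as independent would overstate precision. But 75 is a count of sessions, not of forms. No text says that a form is completed at every session, that any nurse answers twice, or how many nurses take part. The attached questionnaire was not available and may settle respondent and frequency. The plan sets only a more than 80% target and states no confidence interval for it, so poor coverage of an interval that assumes independence would be a fault in an analysis that the plan does not contain.

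Nor should one form per nurse be preferred as a remedy. Assume 75 forms, an intra-nurse correlation of 0.3, and 10 or 15 nurses. At a true rate of 70%, moving from all forms to one form per nurse raises the chance of exceeding 80% from about 12% or 8% to 15% or 13%. At a true rate of 90%, it lowers that chance from about 93% or 95% to 74% or 82%. It does worse in both directions.

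**Phase 1.** A reader might also object that one senior nurse applies the device while participating staff answer the questionnaire. The two statements are compatible, and the plan nowhere claims that the result represents nurses in general.

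**Conclusion.** The point holds for the parent endpoint, as a minor matter and a cheap improvement. The direction of the bias is a fair inference from the stated method; its size is unknown, and the documents give no basis for estimating it. The figures above rest on an assumed true rate, assumed shifts and 25 answering families, and show only what such shifts would do. The consequence is limited: this is a secondary endpoint of a pilot, and the step from Phase 1 to Phase 2 depends on the absence of negative findings, not on parental acceptance.

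The nurse questionnaire supports an optional note on record-keeping only, not a finding of error.

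**What to change.** **Parents.** Replace the investigator's questioning, as the source of this endpoint, with a short written form: one per family, given and collected by the Study Coordinator without the investigator present. Report the number of families asked, the number answering, and the proportion accepting with an exact (Clopper-Pearson) 95% interval. The investigator may still collect open comments, reported separately from the endpoint.

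Cost: a one-page form and a few sentences of protocol text, handled by a Coordinator who already stores and de-identifies the data. Downsides: somewhat less conversational feedback, and some bias remains because the Coordinator belongs to the study team. The change has to be made before parents are questioned.

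**Optional, for the nurse questionnaire.** If a Phase 2 nurse may complete more than one form, put a coded nurse ID on each form and keep the code through de-identification. Report the more than 80% result over all forms together with the number of nurses; if an interval is given, cluster it by nurse. A clustered interval is somewhat too narrow when nurses are few. This costs one extra field on the form.
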